10.2 Visit 2 (Day 0, Injection Day Visit or Telephone Contact)

At Visit 2 (Day 0), all subjects in the AAV2-REP1-treated groups will visit the surgical site, and the following assessments will be performed:

- Full ophthalmic examination, including IOP, a slit-lamp examination, lens opacity, and dilated fundus examination
- AE/SAE monitoring
- Concomitant medication, procedures, and treatment review
- Corticosteroid compliance review

It may be necessary for subjects to undergo a pre-surgical workup according to local hospital procedures (e.g., blood draw for anesthetist) which are outside of the protocol-defined assessments. Any assessments performed outside of the protocol will not be collected as part of the study analyses.

Subjects in the AAV2-REP1-treated groups will then undergo vitrectomy and receive a subretinal injection of AAV2-REP1, containing either 1×10^{11} gp or 1×10^{10} gp (see Section 9.4 for details), in their study eye. Subjects will be carefully monitored for the occurrence of AEs during and after the procedure.

Subjects will return to the surgical site for Visit 3 (post-operative Day 1). Visit 4, post-operative Day 7, may occur at the surgical site or the host site depending on the clinical status of the subject.

Subjects in the Control group will receive the Visit 2 (Day 0) Telephone Call at the agreed upon date and time. Sites will conduct the following assessments during the telephone call:

- AE/SAE monitoring
- Concomitant medication, procedures, and treatment review

10.3 Visit 3 (Day 1 Post-Operative Visit)

At Visit 3 (Day 1), subjects in the AAV2-REP1 groups will return to the surgical site for a post-operative visit. The following assessments will be performed:

• Vital signs

- Immunoassay sampling (ELISA and cell-based assays only)
- BCVA
- Full ophthalmic examination, including IOP, a slit-lamp examination, lens opacity, and dilated fundus examination
- SD-OCT
- AE/SAE monitoring
- Concomitant medication, procedures, and treatment review
- Corticosteroid compliance review

Subjects will be reminded of the requirement to use barrier contraception for a period of 3 months from the time of treatment.

Subjects in the Control group will receive the Visit 3 Telephone Call at the agreed upon date and time. Sites will conduct the following assessments during the telephone call:

- AE/SAE monitoring
- Concomitant medication, procedures, and treatment review

10.4 Visit 4 (Day 7 Post-Operative Visit ± 3 Days)

At Visit 4 (Day 7 ± 3 days), subjects in the AAV2-REP1 groups will return for a second post-operative assessment.

For subjects who traveled from a host site (i.e. same site where their Visit 1 Screening/Baseline visit was performed) to a surgical site for their surgical procedure, this visit may occur either at the surgical site or the host site. However, in the event of a postoperative complication or for any other safety reason considered appropriate by the study surgeon and surgical site Investigator, Visit 4 should be conducted at the surgical site. In this case, post-operative follow-up should continue at the surgical site until the surgeon/surgical site Investigator agrees to discharge the subject to the care of the non-surgical site.

The following assessments will be performed:

- Vital signs
- Immunoassay sampling
- •
- BCVA
- Full ophthalmic examination, including IOP, a slit-lamp examination, lens opacity, and dilated fundus examination
- SD-OCT
- AF
- AE/SAE monitoring
- Concomitant medication, procedures, and treatment review
- Corticosteroid compliance review

Subjects in the Control group will receive the Visit 4 Telephone Call at the agreed upon date and time (\pm 3 days of Day 7). Sites will conduct the following assessments during the telephone call:

- AE/SAE monitoring
- Concomitant medication, procedures, and treatment review

10.5 Visit 5 (Month 1 ± 7 Days)

All subjects, regardless of treatment randomisation, will attend their host site (i.e. same site where their Visit 1 Screening/Baseline visit was performed) from Visit 5 onwards. At Visit 5 (Month 1 ± 7 days), the following assessments will be performed for all subjects (assessments can be spread over 2 consecutive days if necessary):

- Vital signs
- Immunoassay sampling

- BCVA
- Microperimetry
- Full ophthalmic examination, including IOP, a slit-lamp examination, lens opacity, and dilated fundus examination
- SD-OCT
- AF
- AE/SAE monitoring
- Concomitant medication, procedures, and treatment review
- Corticosteroid compliance review for treated subjects

10.6 Visit 6 (Month 4 ± 7 Days)

At Visit 6 (Month 4 ± 7 days), the following assessments will be performed (assessments can be spread over 2 consecutive days if necessary):

• Immunoassay sampling

•

```
• BCVA
```

- Contrast sensitivity test
- Colour vision test
- Microperimetry
- Full ophthalmic examination, including IOP, a slit-lamp examination, lens opacity, and dilated fundus examination
- SD-OCT
- AF

- AE/SAE monitoring
- Concomitant medication, procedures, and treatment review

10.7 Visit 7 (Month 8 ± 14 Days)

At Visit 7 (Month 8 ± 14 days), the following assessments will be performed (assessments can be spread over 2 consecutive days if necessary):

- Immunoassay sampling
- •
- BCVA
- Contrast sensitivity test
- Colour vision test
- Microperimetry
- Full ophthalmic examination, including IOP, a slit-lamp examination, lens opacity, and dilated fundus examination
- SD-OCT
- AF
- AE/SAE monitoring
- Concomitant medication, procedures, and treatment review

10.8 Visit 8 (Month 12 ± 14 Days, End of Study Visit)

At Visit 8 (Month 12 ± 14 days), the following assessments will be performed (assessments can be spread over 2 consecutive days if necessary):

- VFQ-25¹
- Vital signs
- Immunoassay sampling
- •
- BCVA
- Contrast sensitivity test
- Colour vision test
- Reading speed test²
- Microperimetry
- Full ophthalmic examination, including IOP, a slit-lamp examination, lens opacity, and dilated fundus examination
- SD-OCT
- AF
- 7-field colour fundus photography (including stereo photographs for fields 1, 2, and 3)

- AE/SAE monitoring
- Concomitant medication, procedures, and treatment review

1. VFQ-25 must be completed by subjects at the beginning of the study visit, prior to any significant interaction with study staff; the questionnaire is used only in languages in which it is validated.

2. The IReST speed reading test is only conducted in languages of which a validated translation is available.

10.9 Early Termination Visit

In the event that a subject discontinues the study at any time, the site should use every reasonable effort to ensure that an ET Visit is conducted. The following assessments should be performed:

- VFQ-25¹
- Vital signs
- Immunoassay sampling
- •
- BCVA
- Contrast sensitivity test
- Colour vision test
- Reading speed test (if applicable)²
- Microperimetry
- Full ophthalmic examination, including IOP, a slit-lamp examination, lens opacity, and dilated fundus examination
- SD-OCT
- AF
- 7-field colour fundus photography (including stereo photographs for fields 1, 2, and 3)
- AE/SAE monitoring
- Concomitant medication, procedures, and treatment review

1. VFQ-25 must be completed by subjects at the beginning of the study visit, prior to any significant interaction with study staff; the questionnaire is also used only languages in which it is validated.

2. The IReST speed reading test is only conducted in languages in which a validated translation is available.

10.10 Unscheduled Visits

If clinically indicated, subjects may need to return to the site for an unscheduled visit. At a minimum, the following assessments will be performed.

• BCVA

- Full ophthalmic examination, including IOP, a slit-lamp examination, lens opacity, and dilated fundus examination
- SD-OCT
- AF
- AE/SAE monitoring
- Concomitant medication, procedures, and treatment review

11 ASSESSMENT OF EFFICACY

For all visits, an attempt should be made to perform all procedures in both eyes, as described in Table 3. If the subject is unable to complete a procedure due to poor vision in either eye, this should be clearly documented in the source documentation and that procedure can be missed for that eye. In the case that an assessment is missed, the reason should be clearly documented in the source notes.

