Loss of visual acuity (VA) has been observed post-treatment with AAV2-REP1. This VA loss was determined by investigators to be plausibly related to the administration of AAV2-REP1, however without definitively attributing the cause to either the study procedure or the GTMP. Loss of VA is, therefore, considered a Potential Risk of AAV2-REP1 treatment, in addition to the above-described potential and anticipated surgical risks. See the Investigator's Brochure for AAV2-REP1 for further details.

Thus, although there are risks associated with the administration of the study treatment via vitrectomy and retinal detachment, the potential for benefit in the form of improved VA potentially provided to subjects with CHM following treatment with AAV2-REP1 provides an acceptable benefit-risk profile for participation in this study.

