11.3 Best Corrected Visual Acuity

To evaluate changes in VA over the study period, BCVA will be assessed for both eyes using the ETDRS VA chart at the times indicated in Table 3.

The BCVA test should be performed prior to pupil dilation, and distance refraction should be carried out before BCVA is measured. Initially, letters are read at a distance of 4 metres from the chart. If <20 letters are read at 4 metres, testing at 1 metre should be performed. BCVA is to be reported as number of letters read correctly by the subject. At the Screening/Baseline Visit, eyes with a BCVA of 34-73 ETDRS letters (equivalent to worse than or equal to 6/12 or 20/40 Snellen acuity, but better than or equal to 6/60 or 20/200 Snellen acuity) will be eligible for the study.

If a subject cannot read any letters on the BCVA chart, the subject will be tested for finger counting, hand movements or light perception. Refer to the Site Operations manual for full details.

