13.2 Procedure for Accounting for Missing Data

All reasonable efforts will be made to obtain complete data for both eyes on all subjects. However, missing observations may occur. Management of dropout and missing observations will depend on their nature and frequency.

For binary efficacy endpoints (including the primary efficacy endpoint), missing data will be imputed as failure, to be conservative. For the continuous efficacy endpoints, the last observation carried forward (LOCF) approach will be utilized for handling missing data.

To evaluate the robustness of the results of the main analyses, sensitivity analyses of the primary and secondary endpoints will be performed. These analyses will include different imputation methods on different analysis sets and will be described in detail in the Statistical Analysis Plan.

Safety data will be analysed on observed data. Missing data will not be imputed.

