| Study Day/Visit Window | Screening/ Baseline ^f | Day 0 Injection Day | Day 1 Post op | Day 7 Post op ± 3d | Month 1 ± 7d | Month 4 ±7d | Month 8 ±14d | Month 12 ± 14d | | |
| Concomitant medication, procedures and treatment review | X | Х | Х | Х | Х | Х | Х | Х | Х | Х |

Abbreviations: AE=adverse event; BCVA=best corrected visual acuity; ELISA=enzyme-linked immunosorbent assay: ELISPOT=enzyme-linked immunospot; ET=early termination; IOP=intraocular pressure; SAE=serious adverse event; SD-OCT=spectral domain optical coherence tomography; VFQ-25=25-item Visual Function Questionnaire.

NOTE: An attempt should be made to perform all procedures in both eyes, unless otherwise specified. Each eye should be tested separately. If the subject is unable to complete a procedure due to poor vision in either eye, this should be documented in the source notes and the assessment not completed for that eye.

Assessments with gray shading are to be assessor-masked.

- ^a Visit may be performed over 2 consecutive days if necessary.
- ^b Study Visits 2, 3, and 4 only apply to subjects in the AAV2-REP1 groups. For subjects in the Control group, a telephone contact will be made at Visits 2, 3, and 4, and information regarding AEs/SAEs and concomitant medications, procedures, and treatments will be recorded.
- ^c End of Study Visit.
- ^d An ET visit should be performed if a subject discontinues at any time.
- ^e If clinically indicated, subjects may need to return to the site for an unscheduled visit. At a minimum, all assessments listed will be performed.
- ^f Informed consent must be signed within 12 weeks prior of dosing (Visit 2). The Screening/Baseline Visit must be performed within 8 weeks of dosing (Visit 2). Assessments and procedures conducted in the final visit of the NIGHT study (including the ET Visit) may be used for the Screening/Baseline Visit if the final NIGHT study occurs within 8 weeks prior to dosing (Visit 2).
- ^g Samples will be taken and retained for analyses, if necessary.
- ^h VFQ-25: to be completed only at sites where a validated translation is available. VFQ-25 must be completed by subjects at the beginning of the study visit, before any significant interaction with the study staff.
- ⁱ Weight is assessed for dose calculation for 21-day corticosteroid regimen.
- L

^k In order to capture accurate BCVA values at Visit 1 (Screening/Baseline), the following conditions apply to the BCVA assessment:

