10 EFFICACY ANALYSIS

10.1 Primary Endpoint

The primary endpoint will be calculated as the proportion of subjects with $a \ge 15$ -letter increase from baseline in BCVA at the Month 12 visit. If a subject had BCVA missing at Month 12, the primary endpoint of the subject will be imputed as a failure.

The primary endpoint will be summarized using the summary statistics for categorical data including the 95% CI. The 95% CI for the difference in proportions will be computed using the method of Miettinen and Nurminen.

The primary endpoint will be compared between study arms (high dose vs control, low dose vs control) using the Fisher's Exact test. The primary approach will be the unstratified analysis, and a supportive analysis will be conducted with the Cochran-Mantel-Haenszel approach by stratifying by surgical group. As Fisher's Exact test is overly conservative when the number of events is low, a supportive analysis will be conducted using Fisher's Exact-Boschloo test with a Berger-Boos correction of beta=0.001 (Berger 1994). To maintain the test at 0.05 two-sided level, the reported p-value will be 2 times the one-sided p-value from the Fisher's Exact-Boschloo test.

The primary analysis of the primary endpoint will be based on the ITT population, and supportive analyses will be performed based on the PP population and the randomization population. Knowing the patients at site **and** who had BCVA below 34 ETDRS letters at Month 12 for study eye, if any, will not be the responders of subjects with a \geq 15-letter improvement from Baseline in BCVA at Month 12, these subjects with minor protocol deviation will be included in the supportive analysis based on the PP population (see background information for site **and** in Section 8).

Let p_{high} , p_{low} , and p_{cont} represent proportions of subjects with an improvement (≥ 15 -letter) from baseline in BCVA at Month 12 for treatments of high dose and low dose, and control group, respectively.

The following 2 hypotheses will be tested to compare the proportions between each treatment group (high dose or low dose) and control group at Month 12:

- High dose treatment versus control:
 - $\circ \quad H_{01}: p_{high} = p_{cont} versus H_{11}: p_{high} \neq p_{cont}$
- Low dose treatment versus control:
 - $\circ \quad H_{02}: p_{low} = p_{cont} versus H_{12}: p_{low} \neq p_{cont}$

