10.2 Key Secondary Endpoints

The three key secondary endpoints and the corresponding primary analysis are as summarized and presented by pre-specified order in Table 1.

Biogen /	NightstaRx, Ltd
BIIB111	

The continuous efficacy endpoint will be analyzed by the analysis of covariance (ANCOVA) model including surgical group, baseline value of the assessment, and study arms. Missing data will be handled by the last observation carried forward (LOCF) approach.

The binary efficacy endpoints will be analyzed with the same method used for the primary efficacy endpoint with missing values imputed as failure.

The least square (LS) means, standard error (SE) and 95% CI will be reported for each treatment at each post-randomization visit. Least square mean, SE, 95% CI, and p-value for the between group differences will also be provided.

The primary analysis of the key secondary endpoints will be based on the ITT population, and supportive analyses will be performed based on the PP population and the randomized population. When performing the supportive analysis based on the randomized population, for subjects who do not have any post-baseline assessments, the baseline will be used when LOCF approach is applied (i.e. the change from baseline will be zero). Knowing the patients who had BCVA below 34 ETDRS letters at Month 12 for study eye, if any, will at site not be the responders of subjects with a ≥ 10 -letter improvement from Baseline in BCVA at Month 12, these subjects with minor protocol deviation will be included in the supportive analysis of the secondary endpoint of Proportion of subjects with a ≥ 10 -letter improvement from Baseline in BCVA at Month 12 measured by the ETDRS chart based on the PP population. When performing the supportive analysis based on PP population for the secondary endpoints of (a) Change from Baseline in BCVA at Month 12 measured by the ETDRS chart and (b) Proportion of subjects with no decrease from Baseline in BCVA or a decrease from Baseline in BCVA of <5 ETDRS letters at Month 12 measured by the ETDRS chart, subjects at site who had BCVA below 34 at Month 12 will be excluded from these analyses. The background information for site is described in Section 8.

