10.5 Other Secondary Efficacy Endpoints

For the analysis of the following efficacy endpoints, the same analysis of covariance (ANCOVA) model will be utilized based on the ITT population with missing data handled by the LOCF approach.

- Change from Baseline in BCVA at Months 4, 8 and 12
- Change from Baseline at Month 12 in:
 - Total Area of Preserved AF
 - Distance from Foveal Center (FC) to nearest Border of Preserved AF
- Change from Baseline in the following SD-OCT variables at Month 12:
 - Foveal Subfield Thickness
 - Total Macular Volume
 - Central Horizontal Ellipsoid Width

- Central Ellipsoid Area
- Choroidal Thickness
- Change from Baseline in the following microperimetry variables at Month 12:
 - Mean Sensitivity
 - Bivariate Contour Ellipse Area 63%
 - Bivariate Contour Ellipse Area 95%
- Change from Baseline in contrast sensitivity score at Month 12
- Change from Baseline in colour vision at Month 12
- Change from Baseline in reading speed test at Month 12
 - The reading speed will be calculated using the following formula: [number of words in the text number of misread words] / reading time x 60. The number of words per text is available in Appendix 1: IRest Reading Speed Test, Conversion Table, while the number of misread words and reading time will be collected in the case report form (CRF).
- Change from Baseline in the 25-item VFQ-25 overall score and sub-scale scores at Month 12
 - The VFQ-25 patient questionnaire consists of 25 vision-related questions, each of them pertaining to one of the 11 vision-related subscales. For each subscale, a score is calculated. Scores are between 0 and 100, where a higher value represents better functioning. The overall composite score is calculated as the mean of the sub-scale scores (Mangione 2000).

CONFIDENTIAL

CONFIDENTIAL

Page 27 of 46

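### For the continuous per-eye function tests, SAP 10.5 applies LOCF even when the study eye could not be tested because it sees too poorly

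*Protocol*

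**What the plan says.** Protocol 11 first requires an attempt at all procedures in both eyes. Where the subject cannot complete one, it reads: "due to poor vision in either eye, this should be clearly documented in the source documentation and that procedure can be missed for that eye". The note to the schedule in Protocol 17.1, repeated in SAP Appendix 2, says "this should be documented in the source notes and the assessment not completed for that eye". Neither place gives the eye a score.

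For the other secondary endpoints, SAP 10.5 states that "the same analysis of covariance (ANCOVA) model will be utilized based on the ITT population with missing data handled by the LOCF approach". Its list includes microperimetry, contrast sensitivity, colour vision and reading speed. It makes no exception by reason for the gap.

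Binary endpoints follow a different rule. Protocol 13.2: "For binary efficacy endpoints (including the primary efficacy endpoint), missing data will be imputed as failure, to be conservative". SAP 10.1 says that for a missing Month 12 BCVA "the primary endpoint of the subject will be imputed as a failure", and SAP 10.2 analyses the binary key secondaries "with missing values imputed as failure". BCVA also has its own route at the bottom of the range (Protocol 11.3): "If a subject cannot read any letters on the BCVA chart, the subject will be tested for finger counting, hand movements or light perception".

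On robustness, Protocol 13.2 announces sensitivity analyses for the primary and the secondary endpoints. SAP 10.4 provides them for the primary and key secondary endpoints only.

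**The concern.** A test left undone because the eye sees too poorly is not an unknown result. It says that function lies at or near the bottom of that test's scale. LOCF discards this information and substitutes a value from a time when the eye could still be tested. The gap is caused by the outcome itself, so it cannot be treated like a missed appointment.

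The direction matters because the arms differ in surgical exposure. Protocol 5.4 records that "Loss of visual acuity (VA) has been observed post-treatment with AAV2-REP1" and lists it as a potential risk. Only the treated arms undergo vitrectomy and sub-retinal injection. If untestable study eyes arise more often there, the treated-arm means on these four functional endpoints look better than they should, and no planned sensitivity analysis would show it.

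**Working it through.** **1. The plan's own figures.** The documents give no number for untestable eyes. The nearest stated figures are the power values in Protocol 13.1 for the primary endpoint. Exact enumeration of the two-sided Fisher test at 0.05 gives:
- 56 per arm, 16.7% against 0%: 92.3% (stated: at least 90%).
- 64 per arm with exactly one control responder: 8 or more treated responders are needed, power 85.9% (stated: 85%).

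Both hold. An eye too poor to test is a true non-responder and is already scored as failure, so this point changes neither.

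**2. What the rules do to each test (Protocol 17.1 schedule with SAP 10.5).**

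| Test | Scheduled post-baseline visits | Study eye untestable at Month 12 |
|---|---|---|
| Microperimetry | Months 1, 4, 8, 12, ET | Last earlier value carried |
| Contrast sensitivity, colour vision | Months 4, 8, 12, ET | Month 8 or Month 4 value carried |
| Reading speed | Month 12, ET | Normally nothing to carry |

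Reading speed is taken as a per-eye test because the schedule note says each eye is tested separately. The same gap arises for the other tests if the eye becomes untestable before its first post-baseline test. SAP 10.2 carries baseline forward only for the randomised-population analysis of the key secondaries. SAP 10.5 is silent, so the eye is either omitted or scored as unchanged. Both are wrong for an eye that has lost the function.

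**3. Size.** Let n be the arm size (64 high dose, 32 low dose, 64 control; Protocol 13.1), k the number of untestable study eyes in the arm, and L the carried value minus the lowest score.
- Under LOCF, or scoring as no change, the unadjusted arm mean is too high by k × L / n. L is largest when the carried value equals baseline, so 1/64 (or 1/32) of the baseline-to-floor loss per eye is an upper bound.
- If one eye is omitted and the others have mean change M, the error is M − [(n − 1)M − L]/n = (M + L)/n. This is close to L/n when M is small.
- The error in high dose minus control is (k_high − k_control) × L / 64. Equal counts with equal losses cancel.

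**4. Illustration.** All scores and counts here are assumptions, with a floor of 0 and the carried value equal to baseline. Colour vision is left out because the protocol does not name the test.

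| Test | Assumed L | 1 eye of 64 | 1 eye of 32 | 3 eyes of 64 |
|---|---|---|---|---|
| Reading speed, words/min | 60–140 | 0.9–2.2 | 1.9–4.4 | 2.8–6.6 |
| Contrast sensitivity, log units | 1.0–1.4 | 0.016–0.022 | 0.031–0.044 | 0.047–0.066 |
| Mean sensitivity, dB | 5–15 | 0.08–0.23 | 0.16–0.47 | 0.23–0.70 |

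For example, 3 × 140 / 64 = 6.6 words/min. The last column equals the error in the high-dose comparison only if no control eye is affected.

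**The case against.** The strongest reply is that this touches nothing that carries formal inference, and much of that stands.

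- **Confirmatory endpoints.** A reader might infer that the trial's worst visual outcomes are scored too well throughout. The documents do not support this. The primary and both binary key secondaries count missing as failure; LOCF for them is only a sensitivity analysis (SAP 10.4.1). The four endpoints here lie outside the hierarchy in SAP 10.3.
- **BCVA change.** One might extend the point to the first key secondary, which also uses LOCF. But BCVA is reported as letters read, with testing at 1 metre and then off-chart. An eye reading nothing has an observed result, not a skipped test. No letter value for off-chart results is stated, but Protocol 11.3 refers to a manual that may give one.
- **Severe losses are still visible.** Protocol 12.3.1.2 makes defined losses of 15 letters or more reportable as serious. SAP 11.1 summarises reduced-acuity events by treatment, and SAP 11.8 counts eyes losing 15 letters or more at Month 12.
- **Reasons for missing data.** SAP 13 examines them by treatment group. That is descriptive and does not change the LOCF score.
- **Fellow eyes.** Only the study eye has a 34-letter entry floor, so the rule may apply mostly to fellow eyes, which are not in these arm comparisons. This limits the likely count.
- **Unseen manuals.** The operations manual or reading-centre procedures may record a failed attempt as a floor score. If so, the SAP need only say so.
- **Direction.** That the bias favours AAV2-REP1 is tempting to state as fact. Protocol 5.4 reports acuity loss, not loss to the point of being untestable, and gives no frequency. A split of three treated eyes to none in control would itself be an assumption.

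What remains is the unconditional LOCF rule for these four endpoints, the missing rule when nothing can be carried, and the narrower scope of SAP 10.4.

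**Conclusion.** The point holds for microperimetry mean sensitivity, contrast sensitivity, colour vision and reading speed. Followed as written, the plan gives an untestable study eye an earlier, probably better value, or leaves its handling undefined where there is no post-baseline value. A reader might infer that such eyes are dropped from the ITT analysis. The documents do not say this: ITT membership depends on a post-treatment BCVA, and SAP 10.5 has no rule for the case.

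Under LOCF the effect per eye is at most 1/64 of the score lost in the high-dose or control arm and 1/32 in the low-dose arm. The total depends on a count the documents do not give. A bias towards AAV2-REP1 is plausible, given Protocol 5.4, surgery in the treated arms only and the very slow untreated progression described in SAP 5.5, but it is not established. If no study eye becomes untestable, nothing changes. This is a low-to-moderate priority correction, held with moderate confidence; power and the primary analysis are untouched.

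**What to change.** In SAP 10.5, add a rule for a post-baseline study-eye test that is missing with inability due to poor vision as the documented reason. Assign the lowest score on that test's scale in place of LOCF:
- reading speed: 0 words/min;
- contrast sensitivity and microperimetry mean sensitivity: the scale minimum of each test;
- colour vision: the worst score of the test named in the manual.

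At minimum, pre-specify this as a worst-score or rank-based sensitivity analysis beside LOCF. That would also move SAP 10.4 towards the scope announced in Protocol 13.2. Leave the bivariate contour ellipse areas missing, since inability to test does not define a fixation area. Keep LOCF for other reasons. Make the recorded reason available in the analysis data, and report the number of such eyes by arm and visit.

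The cost is SAP wording and, if the eCRF does not already hold the reason, one reason code. No new assessment is needed. Floor scores add some skew to the ANCOVA, and treated-arm means may come out slightly less favourable.
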